3.2.6 Early Termination

3.2.6.1 Withdrawal of Subjects

Subjects may be withdrawn from treatment or from the study for the following reasons:

- Subject did not experience at least 6 qualifying migraines within 12 weeks after patch and applicator dispensation (Visit 3);
- At their own request or at the request of their legally authorized representative;
- If, in the investigator's opinion, continuation of treatment would be detrimental to the subject's well-being;
- If the subject experiences any AE believed to be possibly or probably related to study drug and severe enough to warrant withdrawal of treatment;
- If the subject starts and continues to use a prohibited drug, as listed in [Section 6.2.11](#);
- If the subject is non-compliant with the study drug, eDiary completion, or any other requirement of this protocol; or
- If a subject becomes pregnant anytime during the study.

Subjects who early terminate from the study after applying study medication, will return for an early termination visit and a two-week safety follow-up visit if they applied any patches. For all subjects who are withdrawn from study drug or from the study, the reason must be recorded on the appropriate source document and on the appropriate CRF. The subject must be followed up to establish whether the reason was an AE, and, if so, this must be reported in accordance with the procedures in [Section 8.3](#). Subjects with ongoing systemic and skin AEs at study termination will be followed until all significant changes have resolved or become medically stable.

To the extent possible, all examinations scheduled and all data normally collected at completion of the study (the final study visit) must be performed on all subjects who receive study drug but do not complete the study according to protocol. These assessments must be done at the time of the subject's early termination visit.

The investigator must make at least three documented attempts (phone, email, etc.) to contact subjects lost to follow-up until the time of database lock. This includes one certified letter sent to the subject's primary place of residence. A copy must be maintained in the source documentation.

3.2.6.2 Replacement of Subjects

Subjects who discontinue after starting treatment but before six months will be replaced to ensure adequate enrollment, i.e., 150 subjects in the study who complete six months and 50 subjects who complete a year.

3.2.6.3 Premature Discontinuation of the Trial

The Sponsor has the right to terminate this study at any time. Reasons for termination of the study may include, but are not limited to, the following:

- The Health Authority or IRB/EC terminates the study;
- The incidence or severity of AEs in this or other studies indicates a potential hazard to subjects;
- Subject enrollment is unsatisfactory;
- The trial is not conducted in accordance with the procedures defined in the approved protocol (i.e., protocol deviations, failure to ensure the quality of the data collected);
- New information on the study drug warrants study termination;
- The discretion of the Sponsor

The IRB/Ethics Committee(s) and Health Authorities should be informed about a premature discontinuation of the trial.

4 STUDY TREATMENTS

4.1 Identity of Investigational Products

4.1.1 M207

The M207 patches will be manufactured by Zosano Pharma in Fremont, CA (see Investigator's Brochure for more information).

4.1.2 Product Description and Patch Application

The Zosano M207 Intracutaneous Microneedle System is a novel drug delivery technology which consists of a disposable titanium patch centered on an adhesive backing with microneedles that are dry-coated with the drug product formulation, and a reusable handheld applicator that ensures that the patch is applied with a defined application speed and energy to the site of administration.

The M207 Intracutaneous Microneedle System is a proprietary disposable patch and a reusable applicator. The zolmitriptan-coated titanium microneedle array (3 cm² array) is attached to a 5 cm² adhesive patch (Figure 8). A magnified image of the zolmitriptan-coated microneedles is shown in Figure 8. The patch system is composed of several parts. The patch is mounted inside a polycarbonate plastic ring with a co-molded desiccant (Figure 9).

The M207 drug product used in CP-2017-001 is packaged in a nitrogen purged foil pouch or cup (see Figure 10). The reusable applicator is shown in Figure 9 and Figure 10 with a lock-out function to avoid accidental firing. The applicator provides a spring-driven piston to apply the patch with consistent impact energy of 0.26 Joules. The user presses the handheld reusable applicator onto the patch ring assembly for attachment, then the applicator is un-locked by twisting the cap. The user applies the patch by pressing the applicator/patch ring assembly onto the skin site and holding it to the arm for 3 seconds (Figure 10).

Figure 8: 5 cm² Patch with Zolmitriptan Coated Titanium Microneedle Array

[figure not shown]

Figure 9: Handheld Gen 6 Patch Ring Assembly and Applicator

[figure not shown]
[figure not shown]

Figure 10: *M207 Patch Application

	
Open the foil pouches or cups (depending on the kit dispensed).

	
Snap one patch-ring assembly onto the applicator.

	
Twist applicator cap clockwise from Position 1 to Position 2 to unlock for patch application.

	
Press applicator downward to apply patch to upper arm. Press down firmly against the skin until you hear a click then hold for 3 seconds. Patches are left on for 30 minutes.

	
Remove the outer ring in order to load and apply the second patch.

	
Repeat all of the above steps to apply second patch next to the first patch.

*See subject training video and instructions for use for exact instructions on how to apply the patches

4.2 Dispensing Clinical Trial Material (CTM) Kits

All subjects in the study will receive open label M207, 3.8 mg to administer as two 1.9 mg patches to treat each qualified migraine during the study.

There are two types of M207 kits for each subject, starter kits and refill kits, clearly labeled and visually distinguishable. Each M207 CTM kit includes either 4 (starter kit) or 8 (refill kit) individual foil pouches or cups. Each pouch or cup contains one patch. The starter kit dispensed on day 1 contains the applicator. Refill kits will be dispensed as needed throughout the study. A replacement applicator will be issued at approximately six months, and or/as needed if a previously dispensed applicator is defective or lost.

Zosano may employ an electronic system for supply management of clinical trial material (CTM) kits. The CTM system, if employed, is for drug supply management purposes only. There is no drug randomization as drug assignment is open-label.

At each medication dispensation visit, after it has been established that a subject continues to qualify for the study, study staff will document the total number of patches dispensed to each subject and unopened (unused) patches returned at each visit in the eCRF and drug accountability records.

4.3 Packaging, Labeling, and Receipt of Supplies

In this study, M207 drug product patches will be open-label.

The M207 patches are individually packaged in foil pouches or cups. There are two types of M207 kits for each subject, starter kits and refill kits, which are clearly labeled and visually distinguishable. Each starter kit contains an applicator and 4 individual foil pouches or cups, and each refill kit contains 8 individual foil pouches or cups. Each pouch or cup contains one patch. The kit labels contain at minimum the manufacturer's name, CTM kit number, storage conditions, and a statement indicating that the study drug is for investigational use only.

The pharmacist or designee will inventory and acknowledge receipt of all shipments of study drug.

Optional Instructions for Use (IFU) Survey

Each starter kit of cup-packaged products include a card inviting subjects to participate in an optional online survey inclusive of questions about their experience with the IFU for the cup-packaged product. The invitation card provides the link to the survey website and states that the survey is voluntary and optional. The card also states that if the online survey is completed, the subject will receive a small stipend. The survey consists of approximately 5 questions to collect information about the clarity of the IFU instructions for application of 2 cup-packaged patches to achieve a full dose.

4.4 Study Drug Stability, Storage, and Retention

M207 patches are stable at 15-30°C. The M207 patches and handheld applicators, packaged in individual subject kits, should be stored at a controlled room temperature (15-30°C). All CTM must be kept in a locked and temperature controlled area with access restricted to designated study personnel.

4.5 Study Drug Kit Administration, Dispensation, Accountability, and Return

The study drug will be dispensed only to qualified subjects included in this study in accordance with the eligibility criteria specified in the study protocol.

Throughout the study, upon eDiary confirmation of each migraine qualifying for treatment, subjects will self-administer the study drug. Study personnel will train subjects on how to apply the patches with the M207 applicator.

The study physician or designee will record the CTM kit numbers dispensed to each subject on the drug accountability record. The designated site monitor will periodically check the supplies of CTM to ensure accountability of used applicators and unused kits. If necessary, subjects may return for unscheduled visits for dispensation of additional drug kits. Subjects should be

instructed to bring all unused patches to every clinic visit. Returned patches may be re-dispensed for use to the same subject; however, all patches must be accounted for on the drug accountability log as returned and re-dispensed. The number of patches dispensed at each visit, date dispensed, the number of patches used, and the number of returned unused patches at each visit will be documented. Any discrepancies between the ‘actual’ number of patches returned versus the ‘expected’ number to be returned will be explained. If a subject did not apply both patches to treat a migraine, the site must document the reason in the subject’s source record.

Final study drug accountability will be completed after the last subject visit. All drug accountability records will be filed in the site file and TMF as appropriate.

At the end of the study, all unused study drug kits and used and unused applicators will be inventoried and returned as per the sponsor’s instructions.

4.6 System Performance

An applicator associated with field observations of atypical appearance or system performance should be returned directly to Zosano Pharma. Return instructions for defective applicators with malfunctions are provided in the M207 Site User Manual. A description of the field observation should accompany the shipment. Only problem applicators will be returned to Zosano Pharma.

4.7 Medication Compliance

The investigator will emphasize the importance of correctly self-administering the study medication each time a qualifying migraine is confirmed through the eDiary. Subjects will be instructed to bring the following items to the clinic visit:

- eDiary
- M207 applicator
- Any unused M207 patches

Subjects may discard used patches. The subject will record information regarding each study drug administration in the eDiary.

5 SAFETY AND EFFICACY ASSESSMENTS

5.1 Safety

Safety assessments will be initiated after the informed consent form (ICF) has been signed and will conclude when the post-study procedures are completed (or early discontinuation).

Safety will be assessed through the following:

- Physical exam including height (at screening and final visit only) and weight
- Vital signs including blood pressure
- Clinical laboratory determinations including serum chemistries and hematological parameters
- 12-lead ECGs
- Assessment of concomitant medications
- All treatment-emergent systemic and skin AEs (TEAEs)
- Subject reported Skin Assessment
- Investigator Skin assessment

5.2 Efficacy

- Pain freedom
- Most bothersome other symptom freedom
- Pain relief
- Nausea freedom
- Photophobia freedom
- Phonophobia freedom
- Rescue medication use
- Migraine recurrence
- Subject satisfaction with treatment as assessed by the Migraine-ACT

6 STUDY PROCEDURES AND SCHEDULE

6.1 Study Schedule

A schedule of study procedures is presented in [Table 10](#).

Table 10: Schedule of Study Procedures

Procedure	VISIT 1 ₁ Screening	VISIT 2 ₁ Start of Run-In	VISIT 3	VISIT 4, 5, 6	VISIT 7	VISIT 8	VISIT 9 Final visit or ET	VISIT 10 Two Week Post Study Visit
	Up to 1 week prior to Run-in	Week -2 (up to -3)	Day 1 (dispense patches)	Month 1, 2, 3	Month 6	Month 9	Month 12	Two Week Safety visit
Day/Visit Windows				Day 28, 56, 84 ± 7 days	Day 168 ± 7 days	Day 252 ± 7 days	Day 336 ± 7 days	14 (+ up to 14) days following final visit or ET
Week				Week 4, 8, 12	Week 24	Week 36	Week 48	Week 50 - 52
Informed Consent	X							
Inclusion/Exclusion/ Eligibility Criteria	X	X	X					
Med History/ Migraine History	X							
Fitzpatrick Skin Scale (subject completed)	X							
Demographics	X							
Physical Exam ₃	X		X		X		X	
Weight/Height (Height only at screen and final visit or ET) ₄	X		X	X		X	X	
Vital Signs ₅	X	X	X	X	X	X	X	X
Lab Chem/Hematology (fasting)	X ₆						X	
Serum or Urine Pregnancy (only for WOCP)	X - Serum		X - Urine	X - Urine	X - Urine	X - Urine	X - Urine	
Drug Abuse Testing	X				X		X	
12-lead ECG	X				X		X	
Train Subject on How to Apply Patches (using demo patches)		X	X					

Procedure	VISIT 1 ₁ Screening	VISIT 2 ₁ Start of Run-In	VISIT 3	VISIT 4, 5, 6	VISIT 7	VISIT 8	VISIT 9 Final visit or ET	VISIT 10 Two Week Post Study Visit
	Up to 1 week prior to Run-in	Week -2 (up to -3)	Day 1 (dispense patches)	Month 1, 2, 3	Month 6	Month 9	Month 12	Two Week Safety visit
Train/dispense eDiary		X	X					
Dispense Study Medication			X	X	X	X		
Study Drug Self-Administration								
Subject eDiary Reported Skin Assessments								
Migraine-ACT (subject completed)				X	X	X	X	
Investigator Skin Assessments				X	X	X	X	X
Monthly phone contacts to subject ⁷								
Collect Unused Patch(es)/Perform Drug Accountabilities ⁸				X	X	X	X	
Collect and Review eDiary data			X	X	X	X	X	
Record Adverse Events	X	X	X	X	X	X	X	X
Record Concomitant Medications	X	X	X	X	X	X	X	X

¹ Visit 1 and Visit 2 may be combined into one visit. On the day of screening procedures, if preliminary entry criteria indicate that the subject is probably eligible, the eDiary can be issued and the subject may begin the run-in period. If during the run-in period, additional information becomes available to exclude the subject (e.g., return of 12-lead ECG or lab results), the subject should be notified of screen failure and instructed to return any provisional eDiary device (if applicable) to the center.

³ Physical exam to include (but not limited to) HEENT, Dermatologic, Neurological, General Appearance, Lymph Nodes, Cardiovascular, Respiratory, Gastrointestinal, and Musculoskeletal

⁴ Weight at each visit; both height and weight to be collected at screening and final visit only (or early termination visit)

⁵ Vital signs include temperature, respiratory rate (RR), blood pressure (BP), and heart rate (HR)

⁶ Clinically significant abnormal values may be repeated to confirm eligibility

⁷ Phone contacts monthly at months 4, 5, 7, 8, 10, and 11 to remind subjects to treat at least two migraine attacks per month and to assess for adverse events and concomitant medication use

⁸ Subjects may return for an unscheduled visit to pick up additional study medication as needed.

All study visits and procedures will be performed according to the Schedule of Study Procedures as listed in [Table 10](#). Subject visits should be scheduled as soon as possible within the specified windows.

Subjects must be fasting (i.e., nothing by mouth for at least 4 hours; drinking water during the 4-hour fast before clinical laboratory assessments is permitted) for all laboratory collections.

6.1.1 Screening (Visit 1): Up to 1 Week Prior to Start of the Run-in Period

In order to determine if a subject meets entry criteria, the following activities and evaluations will be performed during screening. Screening activities may be completed over a period as short as one day or spread out over up to one week. On the day of screening procedures, if preliminary entry criteria indicate that the subject is probably eligible, the eDiary training can be completed, the eDiary can be issued, and the subject may begin the run-in period; i.e., Visits 1 and 2 may be combined. If during the run-in period, additional information becomes available to exclude the subject (e.g., return of 12-lead ECG or lab results), the subject should be notified of screen failure and instructed to return any provisional eDiary device (if applicable) to the center.

The following procedures are to be performed during screening:

- Provide informed consent discussion; collect signed ICF (must be done prior to commencing screening assessments)
- Assess subject eligibility based on inclusion/exclusion criteria
- Record demographics
- Subject will be instructed to complete the Fitzpatrick Skin Scale questionnaire (See [Appendix 1](#))
- Record medical history including migraine history, allergies, and current drug and alcohol use
- Perform PE, including height and weight
- Record vital signs: temperature, respiratory rate (RR), blood pressure (BP), and heart rate (HR)
- Collect blood (4-hr fasting) for clinical laboratory measurements including clinical chemistries and hematology
- Collect blood for serum pregnancy for all women of child-bearing potential (WOCBP)
- Urine drug screen

- Perform 12-lead electrocardiogram (ECG)
- Record concomitant medications taken within 30 days prior to Screening
- Register in the case report form any subject who becomes a screen failure

6.1.2 Run-in Period: 2 Weeks [up to +1 week] Prior to Dispensation of Study Medication through Day 1

The Run-in period can begin on the day screening activities are completed, and should be 14 days in duration prior to Visit 3. However, the run-in period may be extended up to an additional 1 week, to a maximum total of 21 days, to accommodate scheduling and/or to confirm compliance and presence of migraine. The Day 1 visit (Visit 3) should be scheduled as soon as possible after 2 weeks of run-in within the specified window, to determine if a subject still meets entry criteria, including the occurrence of at least one qualifying migraine attack per a 14-day period. The following activities and evaluations will be performed during the Run-in period:

6.1.2.1 First Day of Run-in (Visit 2): Week -2 (up to week -3)

- Record vital signs: temperature, respiratory rate (RR), blood pressure (BP), and heart rate (HR)
- Record concomitant medications
- Record adverse events
- Train the subject on how to apply the patches (using demo patches) and the use of the eDiary
- Record that the subject understands how to apply the patch and can administer a demo patch
- Dispense eDiary
 - Subject declares most bothersome symptom **other than pain** (nausea [with or without vomiting], photophobia, or phonophobia—**that is most bothersome most of the time with their migraines**) and it is entered in the eDiary

6.1.2.2 Daily through Run-in Period (2 weeks [+ up to 1 additional week])

- Subject records daily headache activity in eDiary. If the subject did not experience a headache in the past 24 hours, the eDiary will require the subject to answer whether he/she experienced excessive yawning, mood changes, or excessive fatigue (tiredness).
- Subjects must have at least one qualifying migraine in the last 14 calendar days prior to visit 3 (day 1) in the run-in period to meet eligibility for treatment (see [Section 3.2.4](#) for Eligibility Criteria for Study Treatment)

6.1.3 Day 1 (Visit 3, Dispense Study Medication)

- Perform brief physical exam, including weight
- Record vital signs: temperature, respiratory rate (RR), blood pressure (BP), and heart rate (HR)
- Review run-in eDiary data for subject compliance and eligibility for treatment
- Confirm subject is willing to treat all eDiary-confirmed migraine attacks with study medication, and is willing to consistently perform eDiary completion for up to 12 months
- Record concomitant medications, including medication(s) taken to treat migraine attacks
- Urine pregnancy test for all WOCBP
- Record Adverse events
- Train the subject on how to apply the patch to the upper arm with the applicator and have the subject practice applying the demo patches to his/her arm 2-3 times (more is allowable, if necessary)
- Record that the subject can apply patch(es) with the applicator unaided
- Instruct the subject to apply the patches on the same upper arm for each application
- Reconfirm subject's eligibility based on inclusion/exclusion criteria
- Dispense CTM kit and the applicator
- Provide instructions for scheduling the next visit in one month

- Remind the subject that ergot, another triptan and/or vasoconstrictor drugs are prohibited on the day of patch application prior to applying and within 24-hours post-administration of the patch
- Provide any follow-up eDiary training necessary and re-dispense the eDiary
- Dispense the Subject Skin Grading Card (Appendix 4) and instruct the subject to refer to this card when grading their skin reaction(s)/symptom(s) in the eDiary.

6.1.4 Treatment Phase: Up to 12 Months

Visit 3 will be considered the “Day 1” visit for data capture purposes. Subjects will be instructed to complete the eDiary at the time of each suspected migraine attack. Once the eDiary confirms that the migraine qualifies for treatment, the subject will follow the steps provided to self-administer the study drug. If necessary, subjects may return for unscheduled visits for dispensation of additional drug kits.

The following constitutes a migraine that qualifies for treatment with study drug:

- No medication has already been taken to treat the migraine symptoms on the day of the suspected attack before applying M207.
- Presence of at least two of the following characteristics:
 - Unilateral location
 - Pulsating quality
 - Moderate or severe pain intensity
 - Aggravation by or causing avoidance of routine physical activity (e.g., walking or climbing stairs)
- During headache, at least one of the following:
 - Nausea and/or vomiting
 - BOTH photophobia AND phonophobia

The following procedures are to be started at Day 1 after receiving study medication:

- Using the eDiary, the subject will record the following to confirm the headache meets the qualifications for a migraine:
 - Migraine symptoms and pain assessment
- Once the qualifying migraine has been confirmed, subject self-administers the study drug patches. Patches cannot be applied to a previous application site unless the site is free of redness, swelling, and/or bruising. In addition, patches must not be applied to any area where the skin appears tattooed, sunburned, broken and/or irritated.
- Each set of two patches must be applied next to one another (or one above the other), on the same arm. If any skin appears broken or irritated, subsequent doses will be applied a few inches away from the previously applied patches on the same arm (or both patches on the other arm) to avoid applying in an irritated area.
- Qualifying migraine attacks cannot be treated any earlier than 48 hours after the time of patches application for a previously treated migraine attack.
- Subject will continue to record the following in the eDiary at specified time points as follows:
 - Migraine symptoms and pain assessment at the time of treatment, 30 minutes, 2 hour, 12 hours, 24 hours, and 48 hours post patch application
 - Subject reported skin assessment for bleeding at 30 minutes only
 - Subject reported skin assessment for bruising, swelling, and/or redness (at 30 minutes, 2 hours, 12 hours, 24 hours and 48 hours post patch administration time points only)
 - Subject reported skin pain and skin itching at 48 hours post patch administration
- Dispense the Subject Skin Grading Card (Appendix 4) with the eDiary and instruct the subject to refer to this card when grading their skin reaction(s)/symptom(s) in the eDiary. The Grading Card will include a subject reminder to contact the study physician if he/she experiences any serious or severe skin reaction(s) at any time point or for worsening or non-resolving reactions at approximately 3 days post patches application (at 72 hours). In addition, the eDiary will remind the subject to call the study physician if he/she experiences any skin reaction(s) and/or symptom(s) at the patch application site which worsens rather than improves over approximately a five-day period. If the subject

contacts the study physician at any time point for worsening or non-resolving reactions, the subject must be seen for an unscheduled visit. The skin reaction(s)/symptom(s) will be assessed, recorded as an adverse event in the eCRF and followed to resolution.

6.1.5 Month 1 (Visit 4), Month 2 (Visit 5), Month 3 (Visit 6), Month 6 (Visit 7)

Visits must be scheduled to occur on (or within ± 7 days) of the protocol specified study day, ie, on study days 28 (Month 1), 56 (Month 2), 84 (Month 3), and 168 (Month 6). The following procedures will be performed at each visit:

- Administer the Migraine Assessment of Current Therapy (Migraine-ACT) which is completed by the subject
- Collect any unused patches, perform accountability, and dispense patches with applicator
- Perform physical exam, (Month 6 only) (height does not need to be recorded)
- Record vital signs: temperature, respiratory rate (RR), blood pressure (BP), and heart rate (HR)
- Collect urine for urine pregnancy test for all WOCBP
- Collect urine for drug abuse testing (Month 6 only)
- Perform 12-lead electrocardiogram (ECG) (Month 6 only)
- Ensure subject is dispensed the Subject Skin Grading Card (to be used with eDiary entries).
- Collect and review subject's eDiary data with the subject for the following:
 - Subject compliance with study drug treatment and subject responses in eDiary
- Perform Investigator Skin Assessment (presence of blisters, scaly or flakey skin, erosions or open sores, scarring, hyperpigmentation, bruising, redness, and/or swelling) of upper arm where patches have been applied
- Any cutaneous signs or symptoms found on the investigator skin assessment will be recorded as an adverse event on the eCRF and followed to resolution.
- Record concomitant medications
- Record adverse events. In addition, any skin reaction(s) entered into the eDiary by the subject must also be recorded as an adverse event in the eCRF and followed to resolution.

6.1.6 Month 9 (Visit 8) and Month 12 End of Study Final Visit (Visit 9/or Early Termination)

The Month 9 and 12 visits are to be scheduled on (or within ± 7 days) of the protocol specified study day, i.e., on study days 252 (Month 9) and 336 (Month 12). The following procedures will be performed. If a subject terminates early from the study at any time after applying M207, an Early Termination visit must be scheduled to occur within 7-14 days after the subject's last patch application.

- Administer the Migraine Assessment of Current Therapy (Migraine-ACT) to be completed by the subject
- Collect the applicator, any unused patches, and perform accountability
- Dispense M207 patches (Month 9 only)
- Perform physical exam, including weight and height (Month 12 final visit/or early termination only)
- Record vital signs: temperature, respiratory rate (RR), blood pressure (BP), and heart rate (HR)
- Collect blood (4-hr fasting) for clinical laboratory measurements including clinical chemistries and hematology (Month 12 final visit/or early termination only)
- Collect urine for urine pregnancy test for all WOCBP
- Perform 12-lead electrocardiogram (ECG) (Month 12 final visit/or early termination only)
- Ensure subject is dispensed a Subject Skin Grading Card (at Month 9 only)
- Collect and review subject's eDiary data with the subject for the following:
 - Subject compliance with study drug treatment and subject responses in eDiary
- Perform Investigator Skin Assessment (presence of blisters, scaly or flakey skin, erosions or open sores, scarring, hyperpigmentation, bruising, redness, and/or swelling) of upper arm where patches have been applied
- Any cutaneous signs or symptoms found on the investigator skin assessment will be recorded as an adverse event on the eCRF and followed to resolution.
- Record concomitant medications

- Record adverse events. In addition, any skin reaction(s) entered into the eDiary by the subject must also be recorded as an adverse event in the eCRF and followed to resolution.

6.1.7 Monthly Phone Contacts at Months 4, 5, 7, 8, 10, and 11 (\pm 7 days)

Contact subject each month to assess for adverse events, collect and record concomitant medications and remind subject to continue to treat a minimum of 2 qualifying migraine attacks per month.

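### As written, section 6.1.6 collects the applicator at Month 9 and gives back only patches, and no section provides for re-issuing it, so dosing from Month 9 to Month 12 is at risk

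*Protocol*

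**What the plan says.** - **Protocol 6.1.6 (Month 9, and Month 12 or early termination).** One list serves both visits. It contains "Collect the applicator, any unused patches, and perform accountability" and names no visit for it. The next bullet is "Dispense M207 patches (Month 9 only" and mentions no applicator. The same list does limit other items, for example "Perform physical exam, including weight and height (Month 12 final visit/or early termination only". Blood tests and ECG are limited in the same way, and the skin grading card is limited to Month 9.
- **Protocol 6.1.5 (Months 1, 2, 3 and 6).** The parallel bullet is "Collect any unused patches, perform accountability, and dispense patches with applicator".
- **Protocol 4.2 and 4.3 (kits).** "The starter kit dispensed on day 1 contains the applicator" (4.2). "Each starter kit contains an applicator and 4 individual foil pouches or cups, and each refill kit contains 8 individual foil pouches or cups" (4.3).
- **Protocol 4.2 (replacement).** "A replacement applicator will be issued at approximately six months, and or/as needed if a previously dispensed applicator is defective or lost".
- **Protocol 4.1.2 (use of the device).** "The user presses the handheld reusable applicator onto the patch ring assembly for attachment", and the loaded applicator then drives the patch onto the skin.
- **Protocol 4.5 and 4.7 (accountability).** Returned patches may go back to the same subject. Nothing similar is said of applicators, which are inventoried and returned when the study ends. Subjects are told to bring the applicator to clinic visits.
- **Protocol 3.1, 6.1.4 and 6.1.7 (dosing after Month 9).** Treatment runs for up to 12 months, and the calls at Months 10 and 11 remind subjects to treat at least 2 qualifying attacks per month.

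**The concern.** A bullet with no limit, in a list that limits other bullets, applies at both visits. A site that works through 6.1.6 line by line would therefore take the applicator at Month 9 and send the subject home with patches only. The described method of application needs the device.

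The interval from Month 9 to Month 12 completes the one-year exposure. Long-term safety is the primary objective, and Protocol 3.2.1 requires 50 subjects to complete the full one-year treatment period. Dosing lost there for a procedural reason would thin the data that the trial exists to collect. It would also count against the SAP's compliance measure of at least 2 treated migraines per month, through no act of the subject.

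**Working it through.** The plan gives no figure on this point to reproduce. The check compares the text and then sizes the interval.

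**1. Does the collection bullet apply at Month 9?** The authors of 6.1.6 mark single-visit items in both directions: physical exam, blood tests and ECG for Month 12 or early termination, and patch dispensing and the grading card for Month 9. The applicator bullet has neither mark. On the text, it applies at both visits.

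**2. Is there another route to an applicator at Month 9?**
- Month 9 dispensing bullet: patches only.
- Starter kit: holds an applicator, but is given on Day 1.
- Refill kit: patches only.
- Replacement under 4.2: at about six months, or for a defective or lost device. One that the site has collected is neither.
- Re-dispensing under 4.5: stated for patches only.
- Unscheduled visits (4.5, 6.1.4): for additional drug kits.

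No section provides for re-issuing an applicator collected at Month 9.

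**3. What does the literal reading contradict?** It contradicts treatment for up to 12 months (3.1, 6.1.4), the return of applicators at study end (4.5), the Month 10 and 11 reminders (6.1.7), and the Month 9 patch dispensing in 6.1.6 itself.

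**4. Length of the interval.** Inputs are Month 9 at Day 252 and Month 12 at Day 336, each ± 7 days (6.1.6).
- Nominal: 336 − 252 = 84 days, and 84/336 = 25% of the treatment period.
- Shortest: (336 − 7) − (252 + 7) = 329 − 259 = 70 days.
- Longest: (336 + 7) − (252 − 7) = 343 − 245 = 98 days.

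**5. Attacks affected.** Input is the minimum of 2 treated attacks per month (6.1.7).
- With 28-day study months: 84/28 = 3, and 3 × 2 = 6 attacks, or 12 patches, per subject.
- With the SAP's 30-day months (11.1): 84/30 = 2.8, and 2.8 × 2 = 5.6, so about 6 either way.

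**6. Would the analysis show it?** SAP 11.1 takes duration as last dose date minus first dose date plus 1, from eDiary patch applications. For a subject who stopped at Month 9, that duration would end near Day 252 (245 to 259) instead of near Day 336. The SAP also counts doses. At the minimum rate, 9 study months give 9 × 2 = 18 doses and 12 give 12 × 2 = 24, so such a subject would fall short of the SAP's threshold of 24 doses. The monthly counts of treated migraines would drop as well. By contrast, the disposition table in SAP 7.1 counts subjects who completed 12 months without tying that to dosing. A subject who attended Month 12 without an applicator since Month 9 might be counted there.

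**The case against.** The strongest reply is that collecting need not mean keeping. The same bullet collects unused patches, which 4.5 allows to be given back, and 4.7 has subjects bring the applicator to clinic visits. Handing it in for accountability and taking it home again is a natural reading, and no section says that the site keeps it at Month 9. The later calls would also give a site the chance to notice a subject without a device. This stands: lost dosing is a risk and not a certainty. It does not remove the contradiction, because it relies on sites supplying a step that is written for patches and not for applicators.

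A reader might also infer four stronger things that the documents do not support:
- **That Table 10 conflicts with 6.1.6.** Its row on collecting unused patches is marked identically at Visits 4 to 9. That includes the final visit, where collection of the applicator is not in doubt. Its silence on the device therefore says nothing about Visit 8.
- **That long-term exposure would be overstated.** The SAP's exposure measures rest on recorded doses and would show the shortfall. Only the count of 12-month completers might hide it.
- **That 300 to 1,200 attacks would be lost.** This multiplies 6 to 24 attacks by 50 completers, where 24 = 8 × 3 uses the eligibility ceiling on migraine history. It assumes that every one-year completer attends a site that keeps the device, that nobody notices for 84 days, and that every attack qualifies and would have been treated. It is a worst case and not an estimate.
- **That 6.1.5 is a sound model for Month 9.** It dispenses patches with an applicator at four visits without collecting one. Read just as literally, it issues an extra device each time, which does not fit 4.2.

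**Conclusion.** The point holds as a contradiction in the written procedure. Section 6.1.6 has the applicator collected at Month 9, returns patches only, and has no counterpart elsewhere that puts a device back in the subject's hands, while other sections expect dosing to continue. For a subject whose site keeps the device, the exposed interval is about 84 of 336 days (70 to 98 with visit windows), or about 6 attacks at the protocol minimum.

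Those figures assume that the site follows the list literally, that no device is re-issued before Month 12, and that the subject would otherwise have treated 2 attacks per month. The documents do not say how many sites would read it this way, so no trial-wide loss can be stated. Nor do they support reading this as a planned stop at Month 9, since the list dispenses patches at that visit. It is a stated rule that conflicts with the rest of the protocol, not merely a missing detail.

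**What to change.** Reconcile 6.1.6 with 6.1.5, 4.2 and 4.5 so that they agree on two things: at which visit the applicator is finally collected, and whether the subject leaves the Month 9 visit with a working one. The resolution is the sponsor's to make. The 6.1.5 wording should not simply be copied across, because it is itself loose on when an applicator is issued and needs the same attention.

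The cost is a short wording change in an amendment, or a site memo. It adds no visit, procedure or data item.
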